### **10.4 Analysis Population**

The primary analysis population for efficacy and safety is intent-to-treat (ITT) population, which consists of all participants who were randomized.

### **10.5 Safety Analysis**

AEs will be summarized at the event level and participant level according to severity. Proportions and their exact 95% confidence intervals will be calculated.

### **10.6 Monitoring**

#### **10.6.1 Safety monitoring.**

The occurrence of at least two Grade 3 SAEs that are at least possibly related to study conduct or study treatment (including progression to SCC), or a single Grade 4 or 5 AE that is at least possibly related to study conduct will cause the study to halt enrollment. The study will restart only after a review of available safety data and SAE reports by the safety review team: The AMC Medical Monitor (located at the AMC ODMC), the study chairs ([name] and [name]), HPV Working Group chairs ([name] and [name]) and the AMC statistician ([name]). If consensus about restarting the study is not reached among these members, then the decision will be made by the AMC Executive Committee. This process will be repeated after every two serious and related Grade 3 AEs or after each Grade 4 or 5 AE that is at least possibly related to study conduct or treatment. For unanticipated adverse effects that present an unreasonable risk to participants, the study must be terminated

within 5 days of the determination and not later than 15 days after notification of the event. The study may not be resumed without approval from the FDA and reviewing IRBs.

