## 5.4 Criteria for Discontinuing Study Treatment

The investigator should discontinue the study treatment if there is evidence of Grade 4 AEs at least possibly due to study treatment.

The investigator may discontinue study treatment, at his or her discretion, if the participant experiences Grade 3 AEs at least possibly due to study treatment. Alternatively, study treatment may be held and dose reduced as described in [Section 5.3](#).

Participants who prematurely discontinue treatment should remain in study follow-up according to the schedule of events. If treatment is discontinued prior to Week 16, then the participant should undergo HRA with biopsies for the primary endpoint at Week 20. Off-study treatment for anal HSIL prior to Week 20, other than randomized treatment, should be avoided.

Similarly, participants who prematurely discontinue study treatment administered beginning at Week 24 should undergo HRA with biopsies at Week 44.

Participants should discontinue assigned study treatment (or observation without treatment) if progression of disease is suspected. For example, the pathologist suspects possible superficial invasion or there is worsening of histology, as evidenced by an

endophytic growth pattern and pushing borders, or if the clinician notes suspicious friability, ulceration, mass effect, heaped-up borders, and/or markedly abnormal vascular pattern on HRA. These participants should remain in study follow-up and receive treatment as determined by the site investigator.

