## **7.2 Classification of AEs by Severity and Relationship to Study Drug Administration**

- 7.2.1 Adverse Event: Any unfavorable and unintended sign (including an abnormal laboratory finding), symptom or disease temporally associated with the use of a medical treatment or procedure regardless of whether it is considered related to the medical treatment or procedure (attribution of unrelated, unlikely, possible, probable, or definite).
- 7.2.2 Life-threatening Adverse Event: Any AE that places the subject or subject, in view of the Investigator, at immediate risk of death from the reaction.
- 7.2.3 Serious Adverse Event (SAE): Any AE occurring at any dose that results in any of the following outcomes: Death, a life-threatening AE, inpatient hospitalization or prolongation of existing hospitalization, a persistent or significant disability/incapacity, or a congenital anomaly/birth defect.
- 7.2.4 Please note for hospitalization – All hospitalizations (or prolongation of existing hospitalization) for medical events equivalent to CTCAE Grade 3, 4, 5 must be reported regardless of the requirements for Phase of study, expected or unexpected, and attribution. For example, do not report an admission for pharmacokinetic sampling, but do report an admission for a myocardial infarction.
- 7.2.5 Toxicity: Toxicity is a term NOT clearly defined by regulatory organizations. Toxicity has been described as an AE that has an attribution of possibly, probably or definitely related to investigational treatment. To minimize confusion the NCI would recommend that the term toxicity NOT be utilized for AE reporting purposes. The CTCAE continues to use the term ‘toxicity’ because of familiarity.
- 7.2.6 Unexpected Adverse Event: Any AE that is not listed in available sources including the package insert, the Investigator’s Brochure, or the protocol.
- 7.2.7 Cancer Therapy Evaluation Program Adverse Event Reporting System (CTEP-AERS): An electronic system for expedited submission of AE reports.
- 7.2.8 Attribution: The determination of whether an AE is related to a medical treatment or procedure. Attribution categories:
  - Definite – The AE is clearly related to the investigational agent.
  - Probable – The AE is likely related to the investigational agent.
  - Possible – The AE may be related to the investigational agent.
  - Unlikely – The AE is doubtfully related to the investigational agent.
  - Unrelated – The AE is clearly NOT related to the investigational agent.

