## FOR USE IN CIP STUDIES INVOLVING COMMERCIAL (NON-IND/IDE) AGENTS ONLY

### CIP Commercial Agent Studies: Expedited Reporting Requirements for Adverse Events that Occur in a CIP Non-IND/IDE trial within 30 Days of the Last Administration of a Commercial Imaging Agent

#### FDA REPORTING REQUIREMENTS FOR SERIOUS ADVERSE EVENTS (21 CFR Part 312)

**NOTE:** Investigators **MUST** immediately report to the sponsor (NCI) **ANY** Serious Adverse Events, whether or not they are considered related to the investigational agent(s)/intervention (21 CFR 312.64)

An adverse event is considered serious if it results in **ANY** of the following outcomes:

- Death
- A life-threatening adverse event
- An adverse event that results in inpatient hospitalization or prolongation of existing hospitalization for  $\geq$  24 hours
- A persistent or significant incapacity or substantial disruption of the ability to conduct normal life functions
- A congenital anomaly/birth defect.

Important Medical Events (IME) that may not result in death, be life threatening, or require hospitalization may be considered serious when, based upon medical judgment, they may jeopardize the patient or subject and may require medical or surgical intervention to prevent one of the outcomes listed in this definition. (FDA, 21 CFR 312.32; ICH E2A and ICH E6).

**ALL SERIOUS** adverse events that meet the above criteria **MUST** be immediately reported to the NCI via CTEP-AERS within the timeframes detailed in the table below.

Hospitalization	Grade 1 Timeframes	Grade 2 Timeframes	Grade 3 Timeframes	Grade 4 & 5 Timeframes
Resulting in Hospitalization $\geq$ 24 hrs		10 Calendar Days		24-Hour 5 Calendar Days
Not resulting in Hospitalization $\geq$ 24 hrs	Not required		10 Calendar Days	

**NOTE:** Protocol specific exceptions to expedited reporting of serious adverse events are found in the Specific Protocol Exceptions to Expedited Reporting (SPEER) portion of the CAEPR

Expedited AE reporting timelines are defined as:

- “24-Hour; 5 Calendar Days” - The AE must initially be reported via CTEP-AERS within 24 hours of learning of the AE, followed by a complete expedited report within 5 calendar days of the initial 24-hour report.
- “10 Calendar Days” - A complete expedited report on the AE must be submitted within 10 calendar days of learning of the AE.

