**Table 7-A: Routine AE reporting requirements by grade and relationship to study agents**

Relationship to Study Agents	Grade 1 or 2	Grades 3, 4, or 5
Unrelated ( attribution of unrelated or unlikely )	Not Required	Adverse Event Form
Related ( attribution of possible, probable, or definite )	Expected: Expected Toxicity Form Unexpected: Adverse Event Form	Adverse Event Form

Participants withdrawn from the study due to AEs will be followed by the Investigator until the outcome is determined and, when appropriate, additional written reports and documentation will be provided.

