The clinical data entry systems used for AMC studies include the Oncology Patient Enrollment Network, OPEN for enrollment, and Medidata Rave for clinical data entry for enrolled participants; trials activated before September 1, 2020 or that involve only AMC international sites may be reported in AdvantageEDC/Advantage eClinical, a web-based data entry and enrollment system. These data entry systems are programmed to notify the site investigator, protocol chair, AMC medical monitor, and AMC ODMC via email in the event that a site reports an AE that meets expedited reporting criteria to NCI and/or FDA. Additional reporting conditions may be programmed depending on the sponsor reporting requirements of a given protocol (e.g., adverse events of special interest [AESI]). If the site does not follow with an expedited report, the AMC ODMC contacts sites to request compliance with reporting requirements. Additionally, the protocol chair, AMC ODMC, and the AMC medical monitor review reported AEs on a routine basis to identify AEs reported by sites that require expedited reporting. The protocol chair, AMC SWG chairs, AMC group chair, and IND sponsors have general oversight for assuring that routine and expedited adverse reporting requirements are met by the responsible parties.

For studies monitored by CTEP using the Data Mapping Utility (DMU), cumulative protocol- and patient-specific data will be submitted weekly to CTEP electronically via the DMU. For trials

monitored by the NCI's Clinical Data Update System (CDUS), AE information is transmitted electronically to NCI on a quarterly basis. For trials monitored by NCI's Clinical Trials Monitoring Service (CTMS), AE information is transmitted electronically to NCI every two weeks.

**Plans for Assuring that any Action Resulting in a Temporary or Permanent Suspension of an NCI-Funded Clinical Trial is Reported to the NCI Grant Program Director Responsible for the Grant**

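### The first Grade 4-5 safety-halt trigger in Section 10.6.1 omits study treatment, unlike the Grade 3 trigger and the repeat clause: a minor drafting gap

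*Combined protocol and SAP*

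**What the plan says.** Section 10.6.1 states three times which kind of relatedness counts.

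- The Grade 3 trigger is "The occurrence of at least two Grade 3 SAEs that are at least possibly related to study conduct or study treatment".
- The Grade 4-5 trigger, in the same sentence, is that "a single Grade 4 or 5 AE that is at least possibly related to study conduct will cause the study to halt enrollment".
- After a halt and review, the process is to be repeated after every two serious and related Grade 3 events, or "after each Grade 4 or 5 AE that is at least possibly related to study conduct or treatment".

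Once a trigger fires, the study restarts only after the safety review team has looked at the safety data and SAE reports.

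Elsewhere, relatedness is graded against the drug. In Section 7.2.8 the category *possible* reads "The AE may be related to the investigational agent", and the title of Table 7-A refers to "relationship to study agents".

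**The concern.** The opening sentence of the rule treats conduct and treatment as two things joined by *or*, then carries only the first into the Grade 4-5 trigger. The missing attribution is the one the protocol grades. A Grade 4 event recorded as possibly related to 5FU therefore does not match the trigger as worded.

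Taken literally, two drug-related Grade 3 SAEs halt enrolment, while a first drug-related Grade 4 event or a first drug-related death does not. No rationale is given for that ordering. What is at stake is whether the halt and team review at such an event are automatic or left to judgement. Sites and the safety team should not have to debate whether the rule has fired.

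**Working it through.** **1. The clauses side by side (Section 10.6.1)**

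| Clause | Events needed | Relatedness named |
|---|---|---|
| Grade 3, first trigger | two or more SAEs | conduct or treatment |
| Grade 4-5, first trigger | one AE | conduct only |
| Grade 3, repeat | every two serious AEs | *related*, object not stated |
| Grade 4-5, repeat | each AE | conduct or treatment |

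The Grade 4-5 first trigger is narrower in attribution only. It is wider in needing one event rather than two, and any AE rather than an SAE.

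**2. Does another rule fill the gap?**

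- Section 5.4 acts on the individual: "The investigator should discontinue the study treatment if there is evidence of Grade 4 AEs at least possibly due to study treatment".
- Section 7.3.3 requires expedited reporting of serious Grade 4-5 events: "The AE must initially be reported via CTEP-AERS within 24 hours of learning of the AE".
- Appendix VIII gives alerts ("These data entry systems are programmed to notify the site investigator, protocol chair, AMC medical monitor, and AMC ODMC via email"), medical monitor review of every SAE received, DSMB oversight, and a suspension process that starts when suspension is under consideration.
- The end of 10.6.1 requires termination for unanticipated effects that present an unreasonable risk. It is not limited to study conduct, but it needs a determination and covers only unanticipated effects.

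None of these is an automatic halt with restart conditional on team review.

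**3. Remaining 5FU exposure at the version 8.0 date (02AUG2023)**

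Inputs from the documents:
- about 1 accrual per month (10.1);
- main enrolment closed 01JUL2023 (1.2);
- 16-week dosing, last dose by Week 19 (5.3.1);
- cross-over 5FU in Weeks 24-40 (Synopsis);
- regression at most 10% (10.3), so 0.90 still have HSIL.

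Assumptions: 1:1 allocation (0.5 per arm per month), 30.44 days per month, uniform entry, no early stopping, 50%-100% cross-over uptake, constant hazard over a course.

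Number of people = days in window × 0.5 / 30.44.

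| Group | Low | High |
|---|---|---|
| On initial 5FU | randomised 12APR-01JUL2023: 80 days, 1.31 | 19-week limit, 22MAR-01JUL2023: 101 days, 1.66 |
| On cross-over 5FU (randomised 26OCT2022-15FEB2023: 112 days, 1.84; × 0.90 = 1.66) | 0.83 at 50% uptake | 1.66 |
| Cross-over starts still due (randomised 15FEB-01JUL2023: 136 days, 2.23; × 0.90 = 2.01) | 1.01 at 50% uptake | 2.01 |
| People | 3.15 | 5.33 |

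The third row, about 1 to 2 people, is what a halt on enrolment mainly governs, because cross-over participants are enrolled into Segment C (3.4.3).

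Most of the others are part-way through dosing. Mean share of a course remaining:
- initial 5FU, low: (0 + 80)/2 = 40 days of 112 = 0.357;
- initial 5FU, high: (0 + 101)/2 = 50.5 days of 133 = 0.380;
- current cross-over: 0.50;
- not yet started: 1.

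Full-course equivalents:
- low: 1.31 × 0.357 + 0.83 × 0.50 + 1.01 = 0.47 + 0.41 + 1.01 = 1.89;
- high: 1.66 × 0.380 + 1.66 × 0.50 + 2.01 = 0.63 + 0.83 + 2.01 = 3.47.

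**4. Chance of at least one related Grade 4-5 AE**

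The documents give no rate, so the risk per course *p* is assumed. Chance = 1 − (1 − *p*)^*n*.

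| Assumed *p* | *n* = 1.89 | *n* = 3.47 |
|---|---|---|
| 0.5% | 0.9% | 1.7% |
| 1% | 1.9% | 3.4% |
| 2% | 3.7% | 6.8% |
| 5% | 9.2% | 16.3% |

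The course equivalents scale with accrual: 0.9-1.7 at 0.5 per month and 3.8-6.9 at 2 per month.

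**The case against.** The strongest reply is that the paragraph corrects itself. The repeat clause applies to each Grade 4-5 event related to conduct or treatment, and *each* can include the first. The drafting is loose throughout (the Grade 3 part of the repeat clause gives no object for *related*), so *study conduct* may be shorthand for both. As evidence of intent this stands: no sensible safety team would halt at a second drug-related Grade 4 event and ignore the first. As a repair it is incomplete, because a process that is to be *repeated* presupposes that it has already run once.

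The second reply is that the triggered action is to halt enrolment, and main enrolment had closed before version 8.0. That largely stands. It leaves the Segment C starts; participants already on 5FU are not stopped by a halt on enrolment.

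Three stronger readings are tempting and are not supported:

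- A reader might infer that drug-related Grade 4-5 events escape oversight. They do not. The medical monitor and study chairs sit on the safety review team, and the protocol chair and medical monitor are alerted to events that meet expedited criteria. The termination rule at the end of 10.6.1 is stronger than a halt where it applies.
- A reader might infer that drug-related events were exempted on purpose. The repeat clause contradicts this.
- A reader might charge a full course of risk to all 3.1 to 5.3 people on or due to start 5FU, which gives 3.1%-5.2% at a 1% risk. That overstates the exposure of people already part-way through dosing.

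**Conclusion.** The inconsistency is real and sits in an operative safety rule. As worded, a first 5FU-related Grade 4 or 5 AE does not start the automatic halt and team review. It is an unintended drafting omission, and its severity is minor.

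The practical effect under version 8.0 is about 1-2 remaining cross-over starts and about 1.9-3.5 full-course equivalents of 5FU. At an assumed 1% risk per course, the chance of a qualifying event is about 1.9%-3.4%. These figures rest on the accrual, allocation, regression, uptake and constant-hazard assumptions listed in the working. They also assume that the first trigger is unused. The documents do not say whether it has fired; if it has, the repeat clause governs and the omission no longer matters.

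**What to change.** In the Grade 4-5 trigger of Section 10.6.1, insert *or study treatment* directly after *study conduct*, so that it matches the Grade 3 trigger and the repeat clause. The cost is three words in one sentence and possibly one additional safety-team review. The primary analysis is unaffected.

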#### 10.6.2 Futility and efficacy halting rules

An interim analysis is planned after 50% of the ITT population has completed assessment for the primary endpoint to assess the futility of achieving a significant result if the study continues and to potentially demonstrate efficacy before all participants are enrolled. For the comparing topical 5-fluorouracil 5% vs observation, group sequential methods will be used to compare efficacy endpoints preserving the overall one-sided significance level of 0.025 for each comparison. To assess superiority of a treatment arm in comparison to observation the Lan-DeMets stopping boundaries will be used. To assess futility, the O'Brien-Fleming futility boundaries will be used. The interim analyses will be reviewed by the AMC Data and Safety Monitoring Board (DSMB) by the 50% point.

**Table 10-A: Statistical test boundaries and associated operating characteristics for testing efficacy of 5-fluorouracil 5% vs. observation**

Analysis	Total Number (%) of Subjects*	$H_0$ (Futility) Bound Z (P-value)	$H_1$ (Efficacy) Bound Z (P-value)	Overall $\alpha$ Spent	Overall $\beta$ (1-power) Spent
1 (Interim)	35 (50%)	0.258 (0.398)	2.963 (0.002)	0.002	0.020
2 (Final)	70 (100%)	1.955 (0.025)	1.955 (0.025)	0.025	0.100

\*Total number of subjects equals the number in 5FU arm plus observation arm.

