Rationale in the context of ANCHOR results: The absolute risk of cancer over the course of randomized therapy (24 weeks) was very low in both arms. There are ongoing randomized controlled trials of HPV therapeutic vaccines that randomize women with cervical HSIL to no treatment for a similar short period. We believe the risk is small and is lessened by interim anoscopic monitoring of participants with the option to remove the participant from the study for fear of imminent progression. Participants who appear at risk for progression to cancer are not enrolled into AMC-088. As of 19NOV2021, no cases of invasive cancer have developed in AMC-088.

Version 8.0 reduces the sample size from 118 to 88. The primary analysis is not changing.

The effect of this sample size change on statistical power is discussed in [Section 10.0](#). The motivation for the change is because of the slow accrual despite multiple strategies to increase enrollment. Enrollment closed as of 01JUL2023.

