## **10.0 STATISTICAL CONSIDERATIONS**

### **10.1 Rate of Accrual**

This study is expected to accrue eight participants per month for a total of 118 participants (50 per arm for observation and 5FU arms and 18 to the imiquimod arm, which closed because of lack of drug availability). However, the rate of accrual has been approximately one participant per month from 2021-2023. With Version 8.0, the sample size has been reduced to 88 participants (35 per arm for observation and 5FU arms and 18 to the imiquimod arm).

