### 10.7 Primary Analyses

The primary analysis population for efficacy and safety is an intent-to-treat (ITT) population, which consists of all participants who are randomized to 5-fluorouracil 5% or observation. The proportion of participants achieving complete response in the 5-fluorouracil 5%, and the proportion of participants with spontaneous regression in the observation arm will be calculated as the number achieving complete response or experiencing spontaneous regression through the primary endpoint visit (Week 20) divided by the number in the intent-to-treat population. For the treatment comparison (topical 5-

fluorouracil 5% vs. observation) the proportions will be compared across sites using stratified Mantel-Haenszel-Cochran tests at the one-sided 0.05 alpha level. This means that participants who drop out or do not provide evaluable data contribute to the analysis since they are included in the denominator, i.e., they are essentially treated as failures.

Since the imiquimod arm was stopped early, we will describe comparisons between imiquimod and observation using only the participants randomized to imiquimod and observation prior to closure of the imiquimod arm. As a secondary objective, imiquimod 2.5% and topical 5-fluorouracil 5% will be compared using a stratified Mantel-Haenszel-Cochran test at the two-sided 0.05 alpha level using participants randomized prior to the closure of the imiquimod arm.

The primary endpoint will include intra-anal HSIL present on cytology or histology. Perianal HSIL will be descriptively reported separately, as well as combined with the primary endpoint. In addition to the primary intent-to-treat analysis (which includes all randomized participants), we will perform a sensitivity analysis that treats participants who receive HSIL treatment other than randomized treatment (or observation participants that receive any treatment) prior to Week 20 as failures; participants who are lost to follow-up or inevaluable are also still treated as failures. We will also perform a per-protocol analysis using the subset of participants who were adherent to the protocol.

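### Version 8.0 keeps an interim at 35 of 70, meant to act before full enrolment, after enrolment had closed; the status of the look and the final threshold need restating

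*Combined protocol and SAP*

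**What the plan says.** Section 10.6.2 states: "An interim analysis is planned after 50% of the ITT population has completed assessment for the primary endpoint". It gives two aims: "to assess the futility of achieving a significant result if the study continues", and "to potentially demonstrate efficacy before all participants are enrolled". For superiority, "the Lan-DeMets stopping boundaries will be used"; for futility, O'Brien-Fleming bounds apply. The error rate is set by "preserving the overall one-sided significance level of 0.025 for each comparison". The Data and Safety Monitoring Board (DSMB) is to review the interim by the 50% point.

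Table 10-A, revised in version 8.0 for the smaller sample, puts the interim at 35 of 70 (5FU plus observation). The interim bounds are Z 2.963 for efficacy and 0.258 for futility; the final bound is 1.955. Alpha spent is 0.002 then 0.025, and beta spent is 0.020 then 0.100.

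Elsewhere in the same version:
- The Summary of Changes dates version 8.0 to 02 August 2023.
- Section 1.2: "Enrollment closed as of 01JUL2023".
- Section 10.1: "the rate of accrual has been approximately one participant per month from 2021-2023". It also gives the previous target of 50 per arm for these two arms.
- Section 10.7 tests the primary comparison by "stratified Mantel-Haenszel-Cochran tests at the one-sided 0.05 alpha level".

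**The concern.** One of the two stated aims could no longer be met on the day the version was issued, because there was no enrolment left to save. The 50% point had also almost certainly passed, yet the bounds were recalculated for exactly that fraction.

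What is at stake is the critical value of the primary test. Three histories are possible: no look, a look under the larger target, or a late look. Each leads to a different final bound, and the plan does not say which applies or that the bounds will be recomputed at the fraction actually observed. If that stays open until the data are in hand, the threshold of a phase III primary test could be settled after the results are known.

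**Working it through.** **1. Reproduce Table 10-A.** O'Brien-Fleming-type Lan-DeMets spending: a(t) = 2[1 − Φ(z(1−α/2)/√t)].
- Efficacy, α = 0.025, t = 0.5: 2.2414/0.7071 = 3.170, so a = 0.0015 and the bound is 2.963.
- Futility, β = 0.10, t = 0.5: beta spent 0.020. With the drift that gives 90% power (3.269), the bound is −2.053 + 3.269 × 0.7071 = 0.258.
- Final bound, with alpha computed as if crossing futility always stops the trial (binding): 1.9555.

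All tabulated bounds reproduce. They require t = 0.50 and binding futility; an efficacy-only design at t = 0.50 has a final bound of 1.969.

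**2. How many were past Week 20 on 02 August 2023?** Week 20 is 140 days, so such a participant enrolled by 15 March 2023. That is 108 days, or 108/30.44 = 3.55 months, before 01 July 2023. I take the planned 70 as the number enrolled.
- At 1 per month: 70 − 3.55 = 66.5, about 66 (fraction about 0.95).
- Range, with the Visit 5 window of ±21 days (2.86 to 4.24 months) and assumed rates of 0.5 to 3 per month: 70 − 4.24 × 3 = 57 to 70 − 2.86 × 0.5 = 69.
- With an assumed further 6 months for batched central pathology at 1 per month: 70 − 9.55 = about 60.
- For 35 still to be outstanding (no pathology lag), the rate would have to be 35/4.24 = 8.3 to 35/2.86 = 12.2 per month.

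**3. A look under the previous target.** 50% of 100 is 50, and 50/70 = 0.714.

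**4. Type I error if the final test uses 1.955.**

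| Look | Interim efficacy bound | Futility | Type I error |
|---|---|---|---|
| None | – | – | 1 − Φ(1.955) = 0.0253 |
| 35 of 70 | 2.963 | binding, 0.258 | 0.0250 |
| 35 of 70 | 2.963 | ignored | 0.0258 |
| 50 of 70 | 2.963 | binding (0.258) or ignored | 0.0254 |
| 66 of 70 | 2.963 | binding (0.258) or ignored | 0.0253 |
| 50 of 70 | 2.409 (recomputed) | binding, 1.17 | 0.0252 |
| 50 of 70 | 2.409 (recomputed) | ignored | 0.0275 |
| 65 of 70 | 2.053 (recomputed) | ignored | 0.0288 |

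**5. Final bound that restores one-sided 0.025.**
- No look: 1.960.
- Look at 50 of 70 that used 2.963 (alpha spent 0.0015), futility non-binding: 1.962.
- Look at 50 of 70 with 2.409: 2.003 efficacy-only, or 1.961 with binding futility at 1.17.
- Look at 65 of 70 with 2.053: 2.060 efficacy-only.

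Under the one-sided 0.05 of Section 10.7, a single test would use 1.645, so that conflict moves the threshold far more than anything above.

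**The case against.** The strongest reply is that the look may already have been taken. If about 66 of 70 were past Week 20, the 50-participant point of the previous target had passed too, possibly while enrolment was open. A reader might infer from Section 10.6.2 that the interim was never done and can never serve its purpose. The documents do not support that; they are silent on its status. What stands is narrower: version 8.0 describes the look as still to come, at a count that fits neither target's history.

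A reader might also infer a material inflation of type I error. That does not follow. The values of 0.0275 to 0.0288 need three things together: an interim bound recomputed at a later fraction, futility ignored, and 1.955 left uncorrected. The plan prescribes no such sequence. Lan-DeMets spending also exists so that bounds can be recomputed at the observed fraction; the plan names the method but does not say it will do so.

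Moving from 1.955 to 1.960 is numerically trivial. Over every possible 35-versus-35 outcome of the unstratified test (pooled, unpooled or Mantel-Haenszel variance), none gives a Z between the two values. The planned test is stratified by site, so this is indicative only.

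Finally, it would go too far to say that a look now could only discard data. The futility aim does not depend on enrolment, and cross-over follow-up runs to Week 44. With about four primary endpoints outstanding, though, little is left for that aim to decide.

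**Conclusion.** The point holds as a defect of specification with a small numerical effect. Version 8.0 plans an interim whose efficacy purpose had lapsed a month earlier, at a count that had almost certainly been passed. Its bounds are valid only for fraction 0.50 with binding futility.

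The lapsed purpose is on the face of the text and needs no assumption. The missed 50% point rests on the stated average accrual and on 70 having been enrolled; it survives every assumed rate up to 8 per month at the nominal visit lag without a pathology delay. If 1.955 is used, type I error is 0.0253 with no look and about 0.0254 with a look at 50 that used 2.963, against 0.025. That the earlier look, if any, used 2.963 is itself an assumption, since the bounds then in force are not given. The reason to act is that the final critical value is not tied to what happened, and that Sections 10.6.2 and 10.7 disagree on the alpha behind it.

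**What to change.** State in Section 10.6.2 whether an unblinded comparison was made, when, and on how many participants.

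- **No look taken:** delete the interim, its stopping purpose and the interim row of Table 10-A, and test once at Z >= 1.960 for one-sided 0.025.
- **Look taken:** report its N and the alpha actually spent, and recompute the final bound at that fraction of 70. State whether futility is binding. For example, the final bound is about 1.962 if 2.963 was used at 50 of 70 with futility non-binding.

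In either case, choose between one-sided 0.025 (10.6.2) and one-sided 0.05 (10.7) in the same edit, before the final data are examined, because the threshold depends on it. The loss-to-follow-up report in Section 10.6.3 uses the same 50% trigger, so its status should be stated too.

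The cost is a few sentences and one table, with no patients and no new data.
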